5.10 Study and site discontinuation

The overall PI has the ability to discontinue the study, at his discretion, if enrollment is unsatisfactory or if the incidence and severity of adverse events put participants' health at risk. In case of study discontinuation, the PI would notify the investigators in the participating centers.

The overall PI may close any study center in case of incomplete or inaccurate data regarding, poor adherence to protocol, or non-compliance with International Conference on Harmonization guideline for Good Clinical Practice.

6. DOSING DELAYS/DOSE MODIFICATIONS

Stringent inclusion and exclusion criteria as well as close monitoring of both serious and non-serious adverse events aim at ensuring the safety of the participants in this study. All AEs will be defined and graded according to the National Cancer Institute – Common Terminology Criteria for Adverse Events (NCI CTCAE) v5.0. Safety monitoring includes physical examination, laboratory assessments, as well as serial interval histories. All serious adverse events and protocol-defined events of interest will be specifically reported. Investigators and the overall PI will review adverse events on a regular basis during the study.

Dose delays and modifications will be made as indicated in the following tables. The descriptions and grading scales found in the revised NCI-CTCAE version 5.0 will be utilized for dose delays and dose modifications. A copy of the CTCAE version 5.0 can be downloaded from the CTEP website http://ctep.cancer.gov/protocolDevelopment/electronic_applications/ctc.htm.

Regarding treatment-related side effects, abemaciclib and MK-6482 have different adverse event profiles related to their therapeutic class. Some of these adverse events overlap. Management of adverse events potentially attributed to all study compounds, guidelines for dose delays or dose modifications should apply to all study drugs. If an adverse event is attributed to a specific compound, management of dose delays or modifications should be done independently.

Examples of events of particular interest, by frequency or severity, related to abemaciclib include neutropenia, diarrhea, elevated liver function tests. Examples of events of particular interest, by frequency or severity, related to MK-6482 include anemia, edema, fatigue, diarrhea, nausea.

In general, adverse events should be managed with appropriate supportive care. Dose modifications or delays have to be considered in case of unacceptable toxicity and ineffective symptomatic treatment, in order to prevent aggravation of toxicities. Decision of dose delays or reduction may occur at any time, at the discretion of the investigator. Interruption of all study compounds during a period longer than 12 weeks should lead to study discontinuation, unless specific approval by the overall PI.

6.1 Dose levels of abemaciclib and MK-6482

Dose adaptations of abemaciclib and/or MK-6482 are permitted following guidelines provided in **Table 5** and **Table 6**. If a patient who, in the judgment of the investigator, is receiving clinical benefit from study therapy requires further dose reduction than is outlined in **Table 5** and **Table 6**, then the investigator must discuss with the PI prior to any further dose reduction. For patients requiring dose reduction(s), re-escalation to a prior dose level is permitted only after consultation with the overall PI.

Table 5. Dose adjustments of abemaciclib (arm 1 and 2)

Dose Level	Abemaciclib Dose (Arm 1)	Abemaciclib Dose (Arm 2, starting dose 150mg)	Abemaciclib Dose (Arm 2, starting dose 100mg)
0	200mg bid	150mg bid	100mg bid

- 1	150mg bid	100mg bid	50mg bid
- 2	100mg bid	50mg bid	-
- 3	50mg bid	-	-

Table 6. dose adjustments of MK-6482 (arm 2)

Dose Level	MK-6482 Dose
0	120mg qd
-1	80mg qd
-2	40mg qd

6.2 General guidelines for dose delays and dose modifications

General guidelines for dose reductions and delays according to non-laboratory and laboratory adverse events are summarized in **Table 7** and **Table 8**, respectively. Hematologic adverse events, thrombotic adverse events, diarrhea, nausea, vomiting, liver function tests and serum creatinine abnormalities are subject to specific guidelines described in the following sections.

In the situation where an adverse event is thought to be related to both study drugs (abemaciclib, MK-6482) in arm 2, recommendation for the management of toxicities related to all study drugs should apply. In the situation where an adverse event requiring is considered related only to abemaciclib or MK-6482 in arm 2, recommendation for the management of toxicities related only to abemaciclib or MK-6482 may apply. If a patient requires omission of more than 25% of doses for one or both study drugs during a cycle for tolerability, then treatment may continue if the investigator determines the patient is receiving clinical benefit.

A cycle is defined as the planned treatment interval of 28 days plus any subsequent delay prior to start of the next cycle. A delay in the start of a cycle due to holidays, weekends, bad weather, or other unforeseen circumstances will be permitted up to 7 days and not counted as a protocol deviation. Dose omissions are allowed within a cycle. Imaging evaluations should continue on schedule regardless of treatment delays or interruptions.

Table 7. General guidelines for dose adjustments and delays related to non-laboratory toxicities in patients treated with abemaciclib and abemaciclib plus MK-6482. These guidelines do not apply to the management of thrombotic adverse events, diarrhea, nausea, and vomiting, interstitial lung disease/pneumonitis which are subject to specific guidelines reported within following sections.

Treatment Related Toxicity	Arm 1 – abemaciclib alone	Arm 2 – Abemaciclib plus MK-6482
Grade 2 toxicity > 7 days not resolving despite appropriate symptomatic treatment	Hold abemaciclib until resolution of toxicity to baseline or grade 1.	Hold abemaciclib and/or MK-6482 until resolution of toxicity to baseline or grade 1.
Grade 3 toxicity	Hold abemaciclib until resolution of toxicity to baseline or grade 1.	Hold abemaciclib and/or MK-6482 until resolution of toxicity to baseline

	Resume abemaciclib at lower dose level.	or grade 1. Resume abemaciclib and/or MK-6482 at lower dose level.
Grade 4 toxicity	Hold abemaciclib until resolution of toxicity to baseline or grade 1. Resume with lower abemaciclib dose level.	Discontinue MK-6482. Hold abemaciclib until resolution of toxicity to baseline or grade 1. Resume with lower abemaciclib dose level.

Table 8. General guidelines for dose adjustments and delays related to laboratory toxicities in patients treated with abemaciclib and abemaciclib plus MK-6482. These guidelines do not apply to the management of hematologic, liver function tests, and serum creatinine abnormalities, which are subject to specific guidelines reported within following sections.

Toxicity	Arm 1 – abemaciclib alone	Arm 2 – Abemaciclib plus MK-6482
Any drug-related grade 3 or 4 laboratory toxicity that does not resolve within 48 hours and considered clinically significant by the investigator	Hold abemaciclib until resolution of toxicity to baseline or grade 1. Resume with lower abemaciclib dose level.	Discontinue MK-6482. Hold abemaciclib until resolution of toxicity to baseline or grade 1. Resume with lower abemaciclib dose level.

6.3 Hematologic adverse events

Hematologic toxicities including neutropenia, leukopenia, anemia, and thrombocytopenia have been observed in patients treated with abemaciclib, and causality has been established. Hematologic toxicities including anemia (on-target effect of MK-6482), lymphopenia, thrombocytopenia have been observed in patients treated with MK-6482.

Complete blood counts should be monitored prior to the start of therapy, at least every 2 weeks for the first 2 months then monthly. These tests may be ordered locally, and performed within 3 business days for each timepoint.

Patients should be monitored closely for signs of infection, anemia, and bleeding. Dose adjustment may be considered for hematological toxicity \geq Grade 3. Hematological toxicities must resolve to baseline or at least Grade 2 prior to the start of each cycle.

Blood cell growth factors are only to be used in a manner consistent with American Society of

Clinical Oncology (ASCO) guidelines. Dosing of abemaciclib must be suspended if the administration of growth factors is required and must not be restarted within 48 hours of the last dose of growth factors having been administered. When restarted, the dose of abemaciclib must be reduced by 1 dose level if a dose reduction for the specific event necessitating the use of the growth factors has not already occurred.

Fever or infection in the presence of severe neutropenia should be managed promptly with broad-spectrum antibacterial therapy, including coverage for enteric (gram-negative and anaerobic) bacteria. If neutropenic fever persists for 5 days despite broad-spectrum antibacterial therapy, empiric antifungal therapy should be initiated. Anemia and thrombocytopenia should be treated supportively and if necessary with red cell or platelet transfusions.

Table 9a. General guidelines for dose adjustments and delays related to non-anemia hematologic toxicities in patients treated with abemaciclib and abemaciclib plus MK-6482.

Toxicity	Arm 1 – abemaciclib alone	Arm 2 – Abemaciclib plus MK-6482
Grade 3	Hold abemaciclib until resolution of toxicity or grade 2. Abemaciclib dose may be reduced by one dose level, at investigator discretion	Hold abemaciclib and/or MK-6482 until resolution of toxicity to grade 2. Abemaciclib dose may be reduced by one dose level, at investigator discretion Resume MK-6482 at lower dose level.
Recurrent grade 3 Grade 3 thrombocytopenia with bleeding Grade 3 neutropenia with body temperature \geq 38.5°C	Hold abemaciclib until resolution of toxicity or grade 2. Abemaciclib dose must be reduced by one dose level.	Hold abemaciclib and/or MK-6482 until resolution of toxicity to grade 2. Abemaciclib dose must be reduced by one dose level. Resume MK-6482 at lower dose level.
Grade 4		

Table 9b General guidelines for dose adjustments and delays related to anemia in patients treated with abemaciclib and abemaciclib plus MK-6482.

Toxicity	Arm 1 – abemaciclib alone	Arm 2 – Abemaciclib plus MK-6482

Grade 3	Hold abemaciclib until resolution of toxicity to grade 2.	Hold abemaciclib and/or MK-6482 until resolution of toxicity to grade 2.
Grade 4	
Hold abemaciclib until resolution of toxicity to grade 2.
 
Transfusion and/or ESA support
 
Abemaciclib dose must be reduced by one dose level.
	
Hold abemaciclib and/or MK-6482 until resolution of toxicity to grade 2.
 
Transfusion and/or ESA support
 
Abemaciclib dose must be reduced by one dose level.
 
Resume MK-6482 at lower dose level.

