5.4 Definition of Dose-limiting Toxicity

For patients treated in arm 2, DLT will be defined as any abemaciclib or MK-6482 related toxicity resulting in discontinuation or dose reduction per the guidelines in the Section 6.2 to 6.87 within the first 28 days of treatment, for which there is no clear alternative explanation (i.e. disease related).

DLTs will be defined as any of the following events not clearly due to the underlying disease or extraneous causes:

- Any death
- Non-hematologic toxicity:
 - Grade 3 or higher
 - Hy's law cases
- Hematologic toxicity (for non-acute leukemia indications):
 - Grade 4 neutropenia for more than 7 days
 - Grade 3 or higher thrombocytopenia with clinically significant bleeding
 - Neutropenic fever

The DLT definition may exclude:

- Grade 3 nausea/vomiting or diarrhea for less than 72 hours with adequate antiemetic and other supportive care
- Grade 3 or higher electrolyte abnormality that lasts up to 72 hours, is not clinically complicated, and resolves spontaneously or responds to conventional medical interventions
- Grade 3 or higher amylase or lipase that is not associated with symptoms or clinical manifestations of pancreatitis

Patients within arm 2 who do not receive at least 80% of the intended abemaciclib plus MK-6482 doses during the first 28 days for reasons other than toxicity, will not be evaluable for DLTs and will be replaced. Once a tolerable dose combination has been determined in arm 2, patients will no longer be replaced in the study.

Dose escalation will proceed within each cohort according to **Table 4**. Dose-limiting toxicity (DLT) is defined above.

Table 4. Dose-escalation scheme

Number of Participants with DLT at a Given Dose Level	Escalation Decision Rule
0 out of 3	Enter 3 participants at the next dose level.
≥ 2	Dose escalation will be stopped. This dose level will be declared the maximally administered dose (highest dose administered). Three (3) additional participants will be entered at the next lowest dose level if only 3 participants were treated previously at that dose.

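### For anemia in arm 2, the growth-factor rule in section 6.3 conflicts with Table 9b, and on one reading of section 5.4 the use of an ESA can decide whether a grade 3 case is a DLT

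*Combined protocol and SAP*

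**What the plan says.** **Section 6.3, text.** The rule limits blood cell growth factors to use under an outside oncology society's guidelines. It then states: "Dosing of abemaciclib must be suspended if the administration of growth factors is required". Restart is barred until 48 hours after the final growth-factor dose. When abemaciclib is resumed, its dose "must be reduced by 1 dose level if a dose reduction for the specific event necessitating the use of the growth factors"; the sentence ends by exempting an event that has already led to a reduction. The section covers all hematologic toxicity, including anemia, which it describes as an on-target effect of MK-6482. It allows red cell transfusion for anemia and attaches no dose consequence to it.

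**Section 6.3, Table 9b (anemia), arm 2.** At grade 3 the only instruction is "Hold abemaciclib and/or MK-6482 until resolution of toxicity to grade 2". The grade 4 row repeats that hold, adds "Transfusion and/or ESA support", makes a one-level abemaciclib reduction mandatory and has MK-6482 resume at a lower level.

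**Section 5.4.** The lead sentence makes a DLT of any drug-related "toxicity resulting in discontinuation or dose reduction per the guidelines" of section 6 within the first 28 days. The section range it cites is misprinted at its upper end but includes 6.3. A list of DLT events follows. Its hematologic items are prolonged grade 4 neutropenia, grade 3 or higher thrombocytopenia with bleeding, and neutropenic fever; anemia is absent.

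**Section 14.3.3.** The MTD is the highest dose with at most 1 DLT among 6 patients in cycle 1.

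**The concern.** Two passages of one section give different instructions for the same patient. A site that gives an ESA for grade 3 anemia finds no dose reduction in Table 9b and a compulsory one in the text. A site that gives an ESA at grade 4 may, by the table, hold MK-6482 alone and resume on recovery to grade 2; by the text it must stop abemaciclib and wait 48 hours after the last growth-factor dose.

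This reaches a co-primary endpoint because the lead sentence of 5.4 turns a section 6 dose reduction into a DLT. With at most 1 DLT allowed in 6, reclassifying one patient can decide whether a dose level passes. Table 2 has only two levels, with none below the starting level, and the arm 2 response cohort is treated at the MTD. Anemia is also a toxicity the two drugs share: section 7.1 gives 69% of any grade with abemaciclib alone and 75% with MK-6482 alone.

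**Working it through.** **1. Rule trace.** Arm 2, cycle 1, drug-related anemia, no earlier reduction for the same event:

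| Case | Reduction required? | DLT under 5.4 lead sentence | DLT under 5.4 list |
|---|---|---|---|
| Grade 3, transfusion or hold only | No | Not from any required reduction | No |
| Grade 3, ESA (if 6.3 covers ESAs) | Yes, 6.3, on restart | Yes, if restarted lower within 28 days | No |
| Grade 4, transfusion | Yes, Table 9b | Yes, if within 28 days | No |
| Grade 4, ESA | Yes, Table 9b | Yes, if within 28 days | No |

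Only the first two rows differ by supportive measure, and only under the lead sentence. The DLT consequence is therefore confined to anemia below grade 4. At grade 4 what remains is a conflict over which drug is stopped and when it may restart.

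**2. Illustration of size.** The plan gives no operating characteristics for its 3+3 rule, so there is no stated figure to reproduce.

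Inputs:
- g, grade 3 anemia rate: 13%, from section 7.1.2. It is an MK-6482 monotherapy rate with no stated time window; no combination rate is given.
- b, DLT rate from all other causes: 10%, assumed.
- f, share of grade 3 anemia cases given an ESA: 0, 0.5 or 1, assumed.

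Treating the two sources as independent and counting every ESA-treated case, the DLT probability per patient is p = 1 − (1 − b)(1 − g·f). By Table 4 a level clears with 0 of 3 DLTs, or with 1 of 3 followed by 0 of 3:

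P(clear) = (1 − p)³ + 3p(1 − p)⁵

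- f = 0: p = 0.100; 0.729 + 0.177 = **0.906**
- f = 0.5: p = 1 − 0.90 × 0.935 = 0.1585; 0.596 + 0.201 = **0.797** (rounded from unrounded terms)
- f = 1: p = 1 − 0.90 × 0.87 = 0.217; 0.480 + 0.192 = **0.672**

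Sensitivity: with b = 20% the three values are 0.709, 0.596 and 0.486. With b = 10%, f = 1 and g assumed anywhere from 5% to 33%, P(clear) runs from 0.824 to 0.314.

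**3. Is the case likely to arise?** At 13%, the chance of at least one grade 3 anemia is 1 − 0.87³ = 0.34 in 3 patients and 1 − 0.87⁶ = 0.57 in 6.

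**The case against.** The best defence is that the two passages add to each other: Table 9b sets actions by grade, and 6.3 adds a condition when a growth factor is used, with its own exception for an event already reduced for. That largely answers the grade 3 mismatch over reduction, provided a site knows that ESAs fall under the rule. No passage says so. It does not remove the conflict over holding MK-6482 alone, or over the 48-hour bar.

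Other points stand and limit the finding:
- Table 9b names an ESA only at grade 4, and 6.3 mentions transfusion for anemia. Nothing suggests that every grade 3 case would get an ESA.
- A transfused patient is not certain to escape a DLT. Section 6.3 lets dose adjustment be considered from grade 3, and section 6 allows reduction at the investigator's discretion. Whether a discretionary reduction counts under the lead sentence is open.
- The root of the DLT problem is that 5.4 gives two definitions without saying which governs. If the list governs, the choice of support has no effect on DLT status.
- Timing dilutes the effect. A reduction takes place only on restart, after recovery and the 48-hour wait, and some restarts would fall after day 28.
- The 13% is an uncertain input. Section 2.3.1 attaches it to a 33% any-grade rate and quotes 75% separately.

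A reader might infer that any cycle-1 anemia becomes a DLT whenever an ESA replaces a transfusion. The mandatory grade 4 reduction in Table 9b and the prior-reduction exception in 6.3 rule that out.

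**Conclusion.** The concern holds in a limited form. Section 6.3 and Table 9b conflict for arm 2 anemia at grades 3 and 4. The effect on DLT counting is confined to cycle-1 anemia below grade 4, and needs three conditions: ESAs count as growth factors, the lead sentence of 5.4 governs, and the lower-dose restart falls within 28 days.

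The fall from 0.906 to 0.797 or 0.672 shows that the ambiguity could matter; it is not a forecast. It rests on a monotherapy anemia rate used as if it were a cycle-1 rate, an assumed 10% background, assumed ESA use, and every such case counting.

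A reader might go further and say that the MTD depends on local supportive-care habit, with the chance of escalation falling from 1.0 to 0.853 at 13% anemia or 0.494 at an assumed 30%. Those figures need no other DLTs at all and a contrast between ESA use in every case and in none. The documents support neither. The correction is still worth making, because the rules as written disagree and one patient can move the MTD decision.

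**What to change.** 1. State in both the 6.3 text and Table 9b, with one instruction, whether the growth-factor rule covers ESAs given for anemia. Reconcile at the same time which drug is held, when it may restart, and whether a reduction follows.
2. State in 5.4 which governs, the lead sentence or the event list, and correct the section range cited there.
3. State in 5.4 whether a reduction triggered only by growth-factor use counts as a DLT, so that DLT status does not depend on the supportive measure chosen.

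The content of the clinical rule is for the sponsor's medical team; the statistical requirement is that the passages agree. The cost is wording in two sections, with no added procedure, visit or patient.

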6.4 Diarrhea, nausea, vomiting

Diarrhea, nausea and vomiting have been described with both study drugs. Guidelines for dose adjustments and delays related to diarrhea, nausea and vomiting are described in **Table 10**.

At enrollment, patients should receive instructions on the management of diarrhea. In the event of diarrhea, supportive measures should be initiated as early as possible. These include the following:

- At the first sign of loose stools, patients should initiate anti-diarrheal therapy (for example, loperamide) and notify the investigator/site for further instructions and appropriate follow-up.
- Participants should be encouraged to drink fluids (for example, 8 to 10 glasses of clear liquids per day)
- Site personnel should assess response within 24 hours
- If diarrhea does not resolve with anti-diarrheal therapy within 24 hours to either baseline or Grade 1, study drug should be held until diarrhea is resolved to baseline or grade 1.
- If diarrhea resolves to baseline or grade 1, participants should resume dosing as outlined in **Table 10**.

In severe cases of diarrhea, measuring neutrophil counts and body temperature and proactively managing diarrhea with antidiarrheal agents is recommended (page 16). In addition, patients with \geq grade 3 diarrhea should be reviewed by a treating physician once per week until the diarrhea has resolved to \leq grade 1.

If diarrhea is severe (requiring IV rehydration) and/or associated with fever or severe neutropenia, broad-spectrum antibacterial therapy, including coverage for enteric (gram-negative and anaerobic) bacteria. If neutropenic fever persists for 5 days despite broad-spectrum antibacterial therapy, empiric antifungal therapy should be initiated. If diarrhea persists after antibiotic treatment, testing for *Clostridium difficile* is indicated as antibiotic therapy might precipitate *C. difficile* infection.

Patients with severe diarrhea or any grade of diarrhea associated with severe nausea or vomiting should be carefully monitored and given IV fluid (IV hydration) and electrolyte replacement. In these patients, electrolytes and renal function should be monitored regularly during the period of IV hydration.

Table 10. General guidelines for dose adjustments and delays related to diarrhea, nausea and vomiting in patients treated with abemaciclib and abemaciclib plus MK-6482.

Toxicity	Arm 1 – abemaciclib alone	Arm 2 – Abemaciclib plus MK-6482
Grade 2 > 24 hours despite appropriate supportive measures	Hold abemaciclib until resolution of toxicity or grade 1. Abemaciclib dose may be reduced by one dose level, at investigator discretion	Hold abemaciclib and MK-6482 until resolution of toxicity to grade 1. Abemaciclib dose may be reduced by one dose level, at investigator discretion Resume MK-6482 at lower dose level.
Any grade requiring hospitalization and/or IV fluids. Recurrent grade 2 despite appropriate supportive measures. Grade 3 or 4.	Hold abemaciclib until resolution of toxicity or grade 1. Abemaciclib dose must be reduced by one dose level.	Hold abemaciclib and MK-6482 until resolution of toxicity to grade 1. Abemaciclib dose must be reduced by one dose level. Resume MK-6482 at lower dose level.

